1.5 Risks and Benefits

The benefits of the study will be to evaluate the efficacy of the differing modes of medication delivery through the adductor canal pain catheter. If optimized, we believe this will allow us to continue to reduce the amount of narcotic medications prescribed following orthopedic surgery.

All components of the multimodal pain regimen are currently safely used in orthopedic patients. There is a theoretical risk of renal damage or GI upset with the use of anti-inflammatory medications, but we have not seen this with our total knee study. There is also the possibility that patients will have uncontrolled pain following surgery. These patients will have IV narcotic medication as a safety net during their hospitalization and will be able to utilize our standard opioid regimen upon discharge.

2 Study Objectives

Primary Objective

The primary objective will be to compare postoperative pain levels between the treatment groups, using the Numerical Rating Scale (NRS).

Secondary Objective

The secondary objectives will be to compare the amount of patient-administered medication use between groups as well as duration of narcotic use between groups.

3 Study Design

This project will be conducted as a three-arm double-blinded, randomized controlled trial comparing differing modes of medication dispersion using the adductor canal pain catheters. The three arms will be a single shot adductor canal block (with saline filled catheter) compared to ropivacaine 0.2% continuous infusion, and ropivacaine 0.2% intermittent bolus infusions. Treatment groups will be assigned to patients using computer-based randomization via the dynamic allocation method of Pocock and Simon. Subjects will be screened in the outpatient clinic setting and those interested and eligible will be consented and enrolled in the trial.

A total of 84 patients will be enrolled in this study. Twenty eight patients will be in each comparison group. After enrollment patients will undergo randomization by the research pharmacy in order to maintain blinding of the surgical team, nursing staff, and patient. The patient will then undergo their surgical procedure and receive a multi-modal pain regimen as described below. All treatment groups will receive the same regimen with the exception of the adductor canal catheter. All of the patients will have the catheter placed in the Post Anesthesia Care Unit following

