surgery and bolused with 10 mL of 0.5% ropivacaine. The pumps will be loaded with saline (single shot adductor canal group), or ropivacaine 0.2%, dispersed in either a continuous infusion (6 mL/hr) or pulsed intermittent bolus (8 mL every 2 hours). All groups will have a patient demand dose of 6 mL/hr for anterior knee pain. The medication for the adductor catheter will be dispersed to the anesthesia team by the research pharmacy. The anesthesia team will place the catheter under ultrasound guidance in the recovery room. They will adjust the delivery mode based on patient randomization. The anesthesia team will record the serial number of the pump at the time of placement.

Questionnaires will be sent electronically to the patient. Results will be collected daily for 14 days postoperatively, followed by weekly questionnaires until they discontinue narcotic medications. Additional questionnaires will be collected at 30 and 60 days postoperatively in order to record pain and KOOS Jr. scores. The questionnaires will be sent in the morning; if a patient fails to fill out the questionnaire by the afternoon, a member of the research team will contact the patient to obtain the data. The questionnaires will document numerical rating scale (NRS) pain scores, information on symptoms of nausea, vomiting, and constipation, and will inquire if the patient is still consuming narcotic medication.

Following discontinuation of the catheter the patient will remove and return the device to the supplier. The supplier will then provide the rate of on-demand usage to the research team by way of device serial number. This information will be stored in Redcap.

Subjects will be withdrawn prior to completion if they ask to be removed from the study. They may also be withdrawn from the study if they have a serious adverse reaction to one of the prescribed medications. Finally, subjects may be withdrawn at the discretion of the treating physician. If subjects are withdrawn early their last recorded pain score will be carried forward until study conclusion in order to perform intention to treat analysis. The study will continue to ascertain duration of narcotic use with weekly questionnaires, until the patient has stopped the medication.

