3.4 Primary Study Endpoints

The primary endpoint will be pain scores, calculated by the Numerical Rating Scale. This score will be collected daily during the hospital examination and by online or phone surveys after discharge. We will calculate the mean difference in recorded pain scores between cohorts. We hypothesize that the intermittent bolus infusion cohort will report improved pain scores compared to continuous infusion catheters.

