3.7 Identification of Source Data

The following source data will be directly recorded on the Case Report Form (CRF) at the pre-op visit and inputted into REDcap, a password protected database.

- Name
- Medical Record Number
- Email address
- Date of Birth, Age
- Gender
- Race
- Weight (lbs), Height (In), BMI
- Previous surgeries? (yes, no)
- Are you taking Nsaids? (yes, no)
- Previous injections (yes, no)
- Baseline NRS score
- Laterality of surgery
- KOOS Jr. Questionnaire
- Device serial number

The following source data will be recorded daily for two weeks using an online questionnaire recorded into REDcap, and continued weekly until discontinuation of narcotic medication. This data will again be collected at 30 and 60 days following the date of surgery.

- Name
- Medical Record Number
- Date of Birth
- How long has it been since your operation? (Less than 1 month, 1-2 months, Greater than 2 months)
- Are you using narcotic medication? (yes/no)
 - What was the date you last consumed narcotic medication? (if no to previous answer)
- How would you rate the pain you have been experiencing? (0-10)

- Have you been experiencing constipation over the past 24 hours? (yes, no)
- Have you been vomiting or had dry-retching over the past 24 hours? (once, twice, three or more times, no)
- Have you been experiencing a feeling of nausea (an unsettled feeling in the stomach and slight urge to vomit) over the past 24 hours? (yes, no)
- KOOS Jr. Questionnaire (only recorded during 1 month and 2 month questionnaires)
- Rate of on-demand catheter use (recorded at final survey only)

4 Subject Selection Enrollment and Withdrawal

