8.6.1 Internal Data and Safety Monitoring Board

Subject Safety

Specific subject safety parameters include the following information: For the first twenty patients in the study, patients will return to the clinic at the two-week postoperative appointment. Documentation will include levels of pain at the site and any other concerns expressed by the patient. The patients will be assessed for any adverse reaction. This data will be submitted to the sponsor for review and the study will continue enrolling additional patients. Adverse events which would result in possible termination of the study include death, life-threatening adverse experience, patient hospitalization due to drug effects, disability and/or incapacity.

For patients #21 through #84, the subject will be instructed to call the orthopedic department to report any concerns. If the patient has any concerns about a potential adverse reaction, the patient will be promptly seen in the orthopedic clinic.

Data Integrity

Data elements to be reviewed include subject inclusion criteria being met and that the transcription of data is accurate and complete. Data elements will be reviewed at a minimum of every 20 patients being collected by the research coordinator and principal investigator.

Subject Privacy

Consenting will take place in the orthopedic department. They will be informed of the study and given the opportunity to be consented to participate. Consent to participate in the study will only be attempted once.

Data Confidentiality

Hard copy data such as consent forms will be stored in locked file cabinets; electronic data will be stored in our secure web-based database (REDCap) that will be designed with the help of the statistician.

Product Accountability

All portions of the multimodal regimen are commercially available.

Study Documentation

Study file management system as directed by the Study File Management Checklists for FDA-Regulated Studies will be utilized where applicable.

Study Coordination

Debriefing will be performed after the first 20 patients to determine if expectations are clear and if educational needs exist. Scheduled meetings will be sent out via departmental email, and meeting outcomes are noted and available to staff.

9 Data Handling and Record Keeping

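### The pain question behind the primary endpoint does not name the operated knee, so pain from other sites may enter the score and make the comparison less sensitive

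*Combined protocol and SAP*

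**What the plan says.** Section 3.4 defines the outcome: "The primary endpoint will be pain scores, calculated by the Numerical Rating Scale". The contrast follows: "We will calculate the mean difference in recorded pain scores between cohorts". Section 3 describes the surveys in the same general terms: "The questionnaires will document numerical rating scale (NRS) pain scores". The primary objective in section 2 speaks of postoperative pain levels without a location.

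The question itself appears once, in the section 3.7 list for the online questionnaire: "How would you rate the pain you have been experiencing? (0-10". The pre-operative list in 3.7 has "Baseline NRS score", also without a site. Laterality of surgery is on that same list but is not linked to the pain item.

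A site is named in two other places:

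- Section 3, on the pump: "All groups will have a patient demand dose of 6 mL/hr for anterior knee pain".
- Section 8.6.1, on the two-week safety check of the first twenty patients: "Documentation will include levels of pain at the site".

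Section 4.1 requires osteoarthritis indicated for knee replacement. Section 4.2 excludes recent daily schedule II narcotic use, intolerance to regimen drugs, revision surgery, uncontrolled diabetes and pregnancy. It does not exclude other painful joints or back pain.

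**The concern.** The arms differ only in what is delivered through a catheter that serves one knee. A patient with a painful other knee, hip or back can answer the question truthfully with a number that reflects pain the catheter does not reach. That part of the score does not respond to the randomised difference.

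At stake is the sensitivity of the primary comparison. Section 7.1 also says the study is to supply data for powering a larger trial, so a spread and a difference that mix knee and other pain would carry into that calculation. Other-site pain cannot be separated out after the data are collected. Section 7.2 plans no baseline adjustment that might absorb stable pain elsewhere, and the baseline score has no site either.

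**Working it through.** **Does any passage supply the site?** The objective, the endpoint, the survey description, the item and the baseline score all name none. The two places that name one govern other things: use of the demand dose, and a safety check in twenty patients. No passage therefore fixes the site for the primary score.

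**The plan's own figures.** 3 × 28 = 84. For three pairwise tests, 0.05/3 = 0.01667, which rounds to the stated 0.0167. Both reproduce; the overall 0.05 is implied. Section 7.1 says there was no power analysis, so no planned power is in dispute.

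**Assumed inputs.** The documents give no pain mean, SD, effect size or rate of other-site pain. Assumed throughout: knee SD 2 and a true knee difference of 1.5 points. From the plan: n = 28 per arm, two-sided alpha 0.05/3.

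**Knee-only item, normal approximation.** Power = Φ(δ/(σ√(2/n)) − z), with z = 2.394. Here σ√(2/n) = 2 × √(2/28) = 0.535, and 1.5/0.535 = 2.806, so power = Φ(0.412) = 0.66.

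**If other-site pain simply adds to the score (no scale limits).** Randomisation balances it in expectation, so the mean difference stays at 1.5. Only the variance grows: σ = √(4 + s²), where s is the SD of the added pain.

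| s | total SD | power |
|---|---|---|
| 0.5 | 2.06 | 0.63 |
| 1.0 | 2.24 | 0.55 |
| 1.5 | 2.50 | 0.44 |

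**If patients report their worst site.** This was simulated with integer scores limited to 0–10, the rank-sum test at 0.0167, 4000 replicates and other-site SD 2. A share q of patients has other-site pain and reports the larger of the two values.

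| Knee means | Other-site mean | Difference, q = 0 | Difference, q = 20% to 50% | Power, q = 0 | Power, q = 20% to 50% |
|---|---|---|---|---|---|
| 3.0 vs 4.5 | 3 | 1.46 | 1.35 to 1.19 | 0.60 | 0.53 to 0.43 |
| 3.0 vs 4.5 | 5 | 1.46 | 1.25 to 0.97 | 0.60 | 0.41 to 0.22 |
| 4.5 vs 6.0 | 3 | 1.48 | 1.41 to 1.30 | 0.59 | 0.57 to 0.51 |
| 5.5 vs 7.0 | 3 | 1.45 | 1.42 to 1.36 | 0.585 | 0.58 to 0.57 |
| 5.5 vs 7.0 | 5 | 1.45 | 1.34 to 1.21 | 0.585 | 0.53 to 0.46 |

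Repeat runs agreed to within about 0.03 in both power and difference.

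**If patients average over sites** (knee 3.0 vs 4.5). The contrast halves in affected patients, so the difference is 1.46 × (1 − q/2): 1.31 at 20% and 1.10 at 50%. Simulation gave 1.32 to 1.09, with power 0.53 to 0.42.

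**If two full ratings are summed and capped at 10** (knee 3.0 vs 4.5). From 20% of patients with other-site mean 3 to 50% with mean 5, the difference goes from 1.40 to 1.23 and power from 0.42 to 0.17. Most of that loss is variance; the shrinkage comes from the ceiling. Adding two full ratings is an extreme way to answer.

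The direction is the same under every model. The mechanism and the size are not.

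**The case against.** The strongest reply is that context already points to the knee. The survey is sent after knee replacement, and its list asks about time since the operation and narcotic use before it asks about pain. Many patients will rate the operated knee unprompted. This stands: other-site pain may enter the score, but the documents do not show that it does or how often.

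A reader might infer that the primary result is biased toward no difference. That depends on how patients answer. Worst-site or averaged ratings shrink the raw difference; additive pain mainly adds noise. Nor is pain elsewhere untreated, because section 3.1 gives all arms the same systemic analgesics.

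A reader might also see a contradiction between the unlocated item and the two passages that name a site. There is none, because those passages do not define the endpoint.

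Three further replies limit the point:

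- The larger losses assume low knee pain, and the worst case has other-site pain averaging above both arms' knee scores. Excluding recent daily schedule II narcotic users makes severe pain elsewhere less likely, without ruling it out.
- Section 3.4 also draws scores from the hospital stay, whose wording is not given. The list in 3.7 may paraphrase the form, though it is written as the question.
- The pilot's variance would mislead a later trial only if that trial changed the item. With the same item, it is the variance that trial needs.

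What survives is that the primary item leaves its site open, and nothing in the plan closes it.

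**Conclusion.** The point holds as a weakness in the primary measure. As worded, the survey item can record pain from outside the operated knee, and nothing in eligibility, endpoint definition or analysis prevents or removes it. The effect is a possible loss of sensitivity. It does not favour any arm, and the documents do not establish a bias of known size.

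Under the assumed inputs with worst-site reporting, power changes by almost nothing at one end (0.585 to 0.57–0.58, knee means 5.5 vs 7.0, other-site mean 3). At the other end it falls from about 0.60 to 0.22 (knee means 3.0 vs 4.5, half of patients with other-site mean 5), and the observed difference drops from 1.46 to 0.97, about one third. These figures treat each patient as giving one score, whereas scores are collected daily for 14 days. They illustrate a range and do not predict this trial.

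Because the trial was sized for feasibility, the power figures do not show that a design target is missed. The case for acting is that the remedy is nearly free now and unavailable once data are collected.

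**What to change.** - In 3.7, reword the item to ask for pain in the knee that was operated on, with the side filled in from the laterality field already collected.
- Use identical wording for the baseline score, the hospital scores, phone contacts and the day-30 and day-60 surveys.
- In 3.4, state that the primary endpoint is NRS pain in the operated knee.

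The cost is one edit to the REDCap item and the hospital form before enrolment. Sample size, treatment and statistical tests are untouched. The only downside is possibly less comparability with any scores collected using an item that names no site. The item also lacks a recall period; that is a separate gap, and filling it would not supply the site.

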3.3 Duration of Participation

Results will be collected daily for 14 days postoperatively, followed by weekly questionnaires until patients discontinue narcotic medication. Additional questionnaires will be collected at 30 and 60 days postoperatively in order to record pain and KOOS Jr. scores.

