3.5 Secondary Study Endpoints

The secondary endpoints will be the amount of medication administered via the patient-controlled function on the adductor catheter as well as duration of narcotic use required in each cohort. We hypothesize that the intermittent bolus cohort will require fewer doses of patient-administered medication and will use narcotic medication for a shorter duration when compared to the continuous infusion and placebo groups.

We will additionally calculate the overall morphine equivalents used in each cohort during their hospitalization, and dividing this by the total number of post-surgical hospitalization hours in order to normalize the data.

Nausea and vomiting will be recorded daily using the postoperative nausea and vomiting scale and compared between groups. Presence of constipation will be a subjective rating by the patient that is also recorded daily. We will compare the post-surgery length of hospitalization between groups. Finally, we will compare patient-reported outcomes using the KOOS Jr. questionnaire.

We hypothesize that the intermittent bolus cohort will use less narcotic mediation and will therefore have lower rates of constipation, nausea and vomiting. Furthermore, we believe this cohort will demonstrate equivalent lengths of stay and patient-reported outcomes as compared to the comparison groups.

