4.1 Inclusion Criteria

1. Age \geq 18 and $<$ 90 years.
2. Willing to participate in the study and competent to provide informed consent.
3. Willing to comply with protocol procedures.
4. Has an underlying diagnosis of osteoarthritis indicated for a total knee arthroplasty.

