4.4.2 Data Collection and Follow-up for Withdrawn Subjects

If subjects are withdrawn from the study prior to completion we will collect the data prior to withdrawal. At the conclusion of the study we will note the number of subjects that were withdrawn from the study as well as the reasons for withdrawal.

5 Study Drug

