7.2 Statistical Methods

Descriptive and Inferential Statistics

Continuous variables will be summarized with the sample mean, median, standard deviation, minimum, 25th percentile, 75th percentile, and maximum. Categorical variables will be summarized with number and percentage of patients. All analysis will be performed on the basis of the intention-to-treat principle. Comparisons of endpoints between the three treatment arms will be made using a Wilcoxon rank sum test (continuous or ordinal endpoints) or Fisher's exact test (categorical endpoints). Missing data will be imputed using either the last observation carried forward method, a regression-based approach, or another method, depending on the extent of missing data. In order to adjust for the three pair-wise comparisons between treatment groups that will be made for each endpoint, we will utilize a Bonferroni correction for multiple testing, after which p-values of < 0.0167 will be considered as statistically significant. All statistical tests will be two-sided.

Primary Hypothesis:

We hypothesize that the intermittent bolus infusion cohort will report improved pain scores compared to continuous infusion catheters and placebo cohorts.

Secondary Hypothesis:

We hypothesize that the intermittent bolus cohort will require fewer doses of patient-administered medication and will use narcotic medication for a shorter duration when compared to the continuous infusion and placebo groups.

Interim Analysis

We will evaluate the first twenty patients. If 50% of the patients are withdrawn from the study for poor pain control or serious adverse reactions to the study medication, then we will close the study early.

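### A patient withdrawn before day 30 has no postoperative KOOS Jr. score, and the plan leaves open whether the preoperative score stands in for it or the patient is dropped

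*Combined protocol and SAP*

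**What the plan says.** **Schedule.** KOOS Jr. is on the list in section 3.7 that opens "The following source data will be directly recorded on the Case Report Form (CRF) at the pre-op visit and inputted into REDcap", so a baseline value exists. After surgery the same section limits it: "KOOS Jr. Questionnaire (only recorded during 1 month and 2 month questionnaires". Section 3.3 gives the days: "Additional questionnaires will be collected at 30 and 60 days postoperatively in order to record pain and KOOS Jr. scores". The daily surveys do not carry it.

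**Use.** Section 3.5 makes it a secondary endpoint: "we will compare patient-reported outcomes using the KOOS Jr. questionnaire". It does not say whether day 30 or day 60 is meant, or whether the score is raw or a change from baseline. It expects the intermittent bolus arm to be equivalent to the others on this measure.

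**After withdrawal.** Section 4.4.2: "If subjects are withdrawn from the study prior to completion we will collect the data prior to withdrawal". Section 3 (Study Design) adds two things: the last pain score is carried forward, and "The study will continue to ascertain duration of narcotic use with weekly questionnaires, until the patient has stopped the medication". Neither concerns KOOS Jr.

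**Missing data and population.** Section 7.2 applies intention to treat to every analysis and says: "Missing data will be imputed using either the last observation carried forward method, a regression-based approach, or another method", the choice depending on how much is missing. Section 7.3 describes the final analysis as taking in the patients who finish the study. No passage gives a missing-data rule for KOOS Jr., and none says whether a baseline value may be carried forward.

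**The concern.** Pain is scored daily after surgery, so carrying a pain score forward usually carries a postoperative value. KOOS Jr. has no postoperative value before day 30. The eligibility criterion reads "Has an underlying diagnosis of osteoarthritis indicated for a total knee arthroplasty", so for this instrument the only earlier score describes the arthritic knee before the operation. Carrying it forward credits a withdrawn patient with no benefit from the replacement. If section 3.5 intends a change score, the patient's change is exactly zero.

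Withdrawal could plausibly differ by arm. Sections 3.6 and 8.5 withdraw patients for uncontrolled or intolerable pain, and one arm's pump holds saline. An arm with more withdrawals would then look worse on function because of a scoring rule. With equal withdrawal, a true difference would be diluted, which favours the equivalence expected in section 3.5. Dropping the same patients, as section 7.3 would, removes those who may have done worst. Section 7.1 intends the study to supply data for powering a larger trial, so KOOS Jr. means and standard deviations mixed with preoperative scores would also mislead if used there.

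**Working it through.** **The plan's own figures.** 0.05 / 3 = 0.0167, as section 7.2 states, and 3 x 28 = 84, as section 7.1 states. There is no power calculation, KOOS Jr. mean, standard deviation (SD) or expected withdrawal rate to reproduce.

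**Values available.** Three are scheduled: baseline, day 30 and day 60. A patient withdrawn before day 30 has one of three, and none after surgery. A patient withdrawn between days 30 and 60 can have a day-30 value.

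**Bias under carry-forward.** Let w1 and w2 be the proportions withdrawn before day 30 in two arms and D the mean gain those patients would have had by the time point analysed, taken as equal in both arms. Each arm mean shifts by -w x D, so the bias in the difference is -D x (w1 - w2). With assumed inputs, on an assumed 0-100 scale:

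- 0.05 x 15 = 0.75 points
- 0.15 x 25 = 3.75 points
- 0.20 x 30 = 6.0 points

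**Effect on the test.** A mean shift does not show what happens to a rank sum test, so this was simulated separately in SD units. The settings were 28 per arm, no true difference, two-sided 0.0167, 6,000 replicates, baseline-to-postoperative correlation 0.4, equal SDs, and withdrawal unrelated to the score. All but the sample size and the test level are assumptions.

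| Withdrawn before day 30 | Spurious difference, D = 1 SD / 2 SD | False-positive rate, D = 1 SD / 2 SD |
|---|---|---|
| 3/28 v 3/28 | 0 / 0 | 1.3% / 0.7% |
| 6/28 v 1/28 | 0.18 / 0.36 SD | 2.8% / 4.4% |
| 8/28 v 1/28 | 0.25 / 0.50 SD | 5.0% / 10.7% |
| 12/28 v 2/28 | 0.36 / 0.71 SD | 9.6% / 27.1% |

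The differences follow from the formula; for example, 5/28 x 1 = 0.18 and 5/28 x 2 = 0.36. With nobody withdrawn the simulated rate was 1.3% to 1.7%.

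**Dilution.** With D = 1.5 SD and an assumed true difference of 0.8 SD, equal withdrawal of 3/28 or 6/28 per arm reduces power from about 67% to 47% or 24%.

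**Bias under completers only.** In each arm the completers' mean differs from the mean of all randomised patients by w x (mean of completers - mean of withdrawn). This is zero only if nobody withdraws or if withdrawn patients would have scored like the rest. The documents give no figure for it.

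**The case against.** The strongest reply is that the plan never assigns last observation carried forward to KOOS Jr. Section 7.2 lists three possibilities, and order in a list is not priority. Only section 3 commits to carry-forward, and only for pain. A rule limited to post-baseline values would leave the score missing. This stands: a reader might infer that the preoperative score will be used, but the documents show only that it may be.

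Second, section 7.3 could exclude these patients, in which case the carry-forward formula does not apply. That also stands, but it replaces one problem with another and contradicts section 7.2.

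Third, section 4.4.2 does not expressly end later collection, and weekly questionnaires continue after withdrawal. True, but their stated purpose is narcotic duration, and they stop when the patient stops the medication. Even if one carried KOOS Jr. at one or two months, only withdrawn patients still taking narcotics would be measured.

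Fourth, a reader might infer that most withdrawals come early. The catheter is removed on postoperative day 4 and daily surveys end at day 14, so this is reasonable, but no passage says it. Failure to complete questionnaires can lead to withdrawal at any time up to day 60, and as-needed opioids in every arm make the number of pain withdrawals hard to predict.

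Fifth, the size is assumed throughout, and the mean bias is zero if withdrawal and gain are equal across arms. The 50% interim rule does not supply a rate: it covers the first twenty patients, without separating arms, and only withdrawals for poor pain control or serious reactions.

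Finally, KOOS Jr. is outside the three aims and comes last among the secondary endpoints of a feasibility pilot. That limits the weight of the point without removing it.

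**Conclusion.** The point holds in conditional form. A patient withdrawn before day 30 has no postoperative KOOS Jr. value under the written follow-up. The plan permits a method that would put the preoperative score in its place, and its population statement would instead drop the patient. Either can bias the comparison if withdrawal differs by arm.

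The size cannot be derived from the documents. Under carry-forward it is 0.75 to 6 points for assumed gains of 15 to 30 points and assumed withdrawal differences of 5 to 20 percentage points. The upper end means between 5 and 6 more early withdrawals among 28 patients in one arm (0.20 x 28 = 5.6). The documents do not support reading this as an expected bias. Nor do they support extending the point to the primary pain endpoint, which has daily postoperative values. It is a worthwhile, inexpensive correction to a secondary endpoint.

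**What to change.** - **Sections 3 and 4.4.2:** send the existing 30- and 60-day questionnaires, with KOOS Jr., to withdrawn patients who agree, whatever their narcotic status.
- **Section 7.2:** state that a preoperative KOOS Jr. score is never carried forward to a postoperative time point. Handle values still missing by multiple imputation, regressing on baseline KOOS Jr., arm and observed pain scores, with an observed-case analysis beside it. Single regression imputation would understate the variance. Say how results are combined across imputed data sets, since the usual rules pool estimates with standard errors, not rank sum p-values.
- **Section 7.3:** reconcile with the intention-to-treat rule so that withdrawn patients stay in the analysis.

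The cost is wording in four places and two existing electronic surveys per consenting withdrawn patient; no new visit, instrument or sample size is needed. Some will not reply. Section 8.4 unblinds patients at withdrawal, so their later answers are unblinded, and a sensitivity analysis should note this. The imputation assumes that withdrawal is explained by the variables in the model, which is open to doubt when pain is the reason; the observed-case result shows only part of that uncertainty. Surveys not sent at days 30 and 60 cannot be recovered, so the change should be made before patients reach those days.
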